5.2.2. Analyses for Continuous Data

Mixed Effect Model Repeat Measurement (MMRM) for Longitudinal Continuous Data:

The fixed effects of treatment, visit, and treatment-by-visit interaction will be included, along with patient as a random effect. Unstructured covariance matrix will be assumed.

When modeling the change from baseline values, the variable of visit will start with the first post-baseline visit, and the actual baseline value will be included as a covariate. At each visit, estimates of mean values and the mean differences between the active treated group and the placebo group will be derived from the model. The corresponding p-values, standard errors and 95% confidence intervals will also be derived from the model.

Below is an example of potential statistical analysis system (SAS) code:

```
PROC MIXED DATA=XXX;
  CLASS SUBJID TREATMENT VISIT;
  MODEL CHGBASE=TREATMENT VISIT TREATMENT*VISIT BASE/ALPHA=0.05 DDFM=KR;
  REPEATED VISIT/SUBJECT=SUBJID TYPE=UN;
  LSMEANS TREATMENT*VISIT/ALPHA=0.05 CL DIFF;
RUN;
```

Analysis of Covariance (ANCOVA) for Non-longitudinal Continuous Data:

The non-longitudinal continuous data will be analyzed by ANCOVA with treatment as the factor. When modelling change from baseline values, the actual baseline value will be included as a covariate. Active dose group will be contrasted versus placebo.

Below is an example of potential SAS code:

```
PROC MIXED DATA=XXX;
  CLASS TREATMENT;
  MODEL CHGBASE=TREATMENT BASE/ALPHA=0.05;
  LSMEANS TREATMENT/ALPHA=0.05 CL PDIFF;
RUN;
```

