6.1.1. Primary Analysis

The primary analysis will be based on the Bayesian analysis outlined in Appendix 4.

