6.1.2. Sensitivity/Robustness Analyses

There are 3 sets of analyses.

Set 1:

The sensitivity analysis will be based sensitivity prior models on the Bayesian analysis outlined in [Appendix 4](#).

Set 2:

- Missing data imputation
 - Observed
 - LOCF
- ANCOVA (see [Section 5.2.2](#))
 - Baseline SDAI as a covariate
 - Baseline SDAI and previous anti-TNF use as covariates

Set 3:

- Missing data imputation – none (Observed).
- MMRM (see [Section 5.2.2](#)) for analysis of change from baseline in SDAI at Weeks 1, 2, 4, 6, and 8.
 - Baseline SDAI as a covariate
 - Baseline SDAI and previous anti-TNF use as covariates

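### The repeated-measures model fits one baseline slope for all visits, so Week 8 may be under-adjusted and lose some precision in the continuous secondary efficacy and PRO analyses and in SDAI sensitivity Set 3

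*SAP*

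**What the plan says.** SAP 5.2.2 describes the longitudinal model in words: "The fixed effects of treatment, visit, and treatment-by-visit interaction will be included, along with patient as a random effect". For change scores it adds that "the actual baseline value will be included as a covariate", and on the covariance it says "Unstructured covariance matrix will be assumed". The SAS code that follows, introduced with "Below is an example of potential statistical analysis system (SAS) code", has the model line "MODEL CHGBASE=TREATMENT VISIT TREATMENT*VISIT BASE/ALPHA=0.05 DDFM=KR" and a REPEATED statement with TYPE=UN. It has no RANDOM statement. Neither the prose nor the code contains a baseline-by-visit term, and no other section adds one.

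The model is used in two places:
- SAP 6.1.2, Set 3, applies it "for analysis of change from baseline in SDAI at Weeks 1, 2, 4, 6, and 8" as a sensitivity analysis of the primary endpoint, with and without prior anti-TNF use as a further covariate.
- SAP 6.2.1 to 6.2.5 and 6.3 use it for change from baseline in SDAI, the four DAS28 versions, hsCRP, the 28-joint counts, PhGA, PAAP, PtGA and HAQ-DI.

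The primary analysis is a different model. SAP 6.1.1 states: "The primary analysis will be based on the Bayesian analysis outlined in Appendix 4".

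**The concern.** A single BASE term forces the regression of change on baseline to be the same one week into treatment as at eight weeks. There is reason to expect otherwise. As the correlation of a score with its own baseline falls over time, the slope of change on baseline moves away from zero. If that happens here, the fitted common slope differs from the Week 8 slope, and part of the variation that baseline could explain at Week 8 stays in the error.

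Precision is what is at stake. The trial plans about 50 completers, and for the endpoints other than SDAI this model is the only listed analysis of change from baseline. For SDAI, Set 3 would adjust for baseline differently from the primary analysis and Set 2. A gap between them could then be read as a missing-data effect when part of it comes from baseline adjustment.

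**Working it through.** **1. Inputs from the documents.** Protocol 9.1 gives 30 active and 20 placebo completers, an SD of SDAI change of 14 in both arms, a difference of 13 and a 5% error rate. Checking these first: SE = 14 × √(1/30 + 1/20) = 4.04, and 13/4.04 = 3.217. Normal-approximation power is Φ(3.217 − 1.960) = 89.6% two-sided and Φ(3.217 − 1.645) = 94.2% one-sided, against a stated figure of over 90% with no sidedness given. The inputs are therefore usable as they stand.

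**2. Inputs the documents do not give (assumptions).** Baseline SDAI SD is 12. The slope on baseline (of improvement, so positive) is equal at all visits, or grows in equal steps from 0.15 to 0.4 or from 0.1 to 0.5. The SD of change is 14 at every visit, or rises as 9, 10.5, 12, 13, 14. Residual correlation is 0.5 or 0.7 for every pair of visits, or 0.8 per two weeks decaying with distance (AR).

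**3. Formula.** Let b be the vector of visit slopes and S the residual covariance. In large samples with complete data, the common slope tends to b_c = (1′S⁻¹b)/(1′S⁻¹1). The Week 8 contrast is the difference in mean change minus b_c times the difference in mean baseline. Compared with visit-specific slopes, its variance is multiplied by

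1 + (b₈ − b_c)² × Var(baseline) / Var(residual at Week 8).

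**4. Worked case, rising SDs, slopes 0.1 to 0.5, correlation 0.5.** Residual variances are SD² − b² × 144: 79.56, 104.49, 131.04, 145.96 and 160. The visit weights in b_c are 0.52, 0.27, 0.12, 0.07 and 0.03, so b_c = 0.182 against 0.5 at Week 8. Inflation is 1 + (0.318)² × 144/160 = 1.091 in variance, or √1.091 = 1.045 in SE.

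**5. Same case with SD 14 at every visit.** The weights are 0.15, 0.16, 0.19, 0.22 and 0.28, which now favour later visits. So b_c = 0.334, and inflation is 1 + (0.166)² × 144/160 = 1.025.

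**6. Range of Week 8 variance inflation.**

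| Slopes, Week 1 to 8 | Visit SDs | Corr. 0.5 | Corr. 0.7 | AR 0.8 |
|---|---|---|---|---|
| equal | either | 1.000 | 1.000 | 1.000 |
| 0.15 to 0.4 | flat 14 | 1.011 | 1.009 | 1.010 |
| 0.15 to 0.4 | 9 to 14 | 1.036 | 1.060 | 1.039 |
| 0.1 to 0.5 | flat 14 | 1.025 | 1.016 | 1.023 |
| 0.1 to 0.5 | 9 to 14 | 1.091 | 1.151 | 1.099 |

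The inflation passes 20% only at the edge of the range. With slopes 0.1 to 0.5, rising SDs and a correlation of 0.8 between every pair of visits, it is 1.228.

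**7. Finite-sample check.** A simulation used 600 trials per setting, 36 and 24 randomised and 15% monotone dropout. The empirical SD of the Week 8 contrast, common slope relative to visit-specific slopes, had these ratios:
- equal slopes: 0.99
- slopes 0.2 to 0.4: 1.01
- slopes 0.1 to 0.5: 1.01 to 1.02
- slopes 0.1 to 0.7: 1.03 to 1.16

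No material bias in the treatment effect appeared.

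**The case against.** The strongest reply is that a common baseline slope is a valid model under randomisation, that nothing in the documents shows the slope grows, and that for SDAI the remedy is largely in the plan already. With complete data, an unstructured model with BASE*VISIT gives the same Week 8 estimate as a Week 8 ANCOVA, and Set 2 specifies that ANCOVA. The only decision rule, in SAP 5.1, belongs to the Bayesian analysis. The code is also labelled an example.

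Most of this stands and limits the weight of the point. Three things remain. The prose describes the same single covariate, so the example label does not settle the matter. Set 2 covers SDAI only, and the other continuous efficacy and PRO endpoints have no Week 8 ANCOVA beside the mixed model. With dropout, Set 2 uses observed cases or LOCF, whereas the mixed model relies on missing at random. Set 3 therefore adds something, and its comparison with Set 2 should not also involve a different baseline adjustment.

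A reader might infer that a common slope is always pulled toward the early visits. It is not: step 5 shows the weights tilting later when visit SDs are flat. The early pull needs SDs that rise over time.

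A reader might also take the patient random effect in the text as a serious fault. It is true that a random intercept cannot be estimated separately beside an unstructured covariance, because the latter absorbs it. But the REPEATED / TYPE=UN code shows which model is meant, so this is a wording mismatch.

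**Conclusion.** The point holds as a minor efficiency improvement. The single slope is certain from the text. The loss is conditional on slopes that grow during treatment, which is plausible but is not a figure in the documents. With baseline SD 12 and Week 8 SD 14, the Week 8 variance is inflated by about 0–3% if visit SDs are flat and by roughly 2–12% in most cases if they rise. It is inflated more only when steep slope growth meets a high correlation between all visits, and not at all if slopes are equal. At the 12% end the loss is equivalent to 50 × (1 − 1/1.12) ≈ 5 of 50 completers. These figures are for SDAI; the documents give no inputs for the other endpoints.

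The documents do not support reading this as a flaw in the primary result. The Bayesian ANCOVA in SAP Appendix 4 and the Set 2 ANCOVA each estimate a Week 8 slope. They do not support a charge of bias either. Nor does the point reach every continuous secondary endpoint: the vital-sign and laboratory endpoints are summarised descriptively under SAP 6.7 and do not use this model.

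**What to change.** In SAP 5.2.2, add BASE*VISIT to the MODEL statement and name the baseline-by-visit interaction among the fixed effects in the prose. Apply this to every analysis that uses the model, including both versions of Set 3. The cost is one term and one sentence, and four degrees of freedom (five slopes instead of one). If the slopes are in fact equal, the price is just under 1% in SE.

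Separately, and as wording only, delete "along with patient as a random effect" so that the text describes the unstructured REPEATED model in the code.

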5.2.3. Analyses for Categorical Data

The frequency and percentage for each category will be presented.

5.2.4. Analyses for Time to Event Data

None.

5.3. Methods to Manage Missing Data

In general, for descriptive statistics missing values will not be imputed. In addition, for safety endpoints missing values will not be imputed. Unless there is an explicit instruction, missing values will be used for lower limits of detection and quantitation.

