 - High sensitivity C reactive protein (hsCRP) ≥ 7 mg/L at screening performed by the central laboratory. Subjects who do not meet this entry criterion but satisfy all other study entry criteria may have serum hsCRP concentration re-tested and, if the repeat hsCRP concentration is ≥ 7 mg/L prior to the baseline visit, will be eligible to enroll into the study provided all other inclusion/exclusion criteria are met.
9. Subjects must be seropositive (rheumatoid factor positive and/or anti-citrullinated protein antibody positive) at the screening visit.
10. Subjects must have been taking oral MTX for at least 3 months at an adequate dose to determine that the subject had an inadequate response to MTX, defined, for the purpose of this study, by the investigator's and subject's opinions that the subject did not experience adequate benefit from methotrexate plus the presence of sufficient residual disease activity to meet the entry criteria. Allowed methotrexate doses are 15 to 25 mg, inclusive, weekly, unless there is documented (in the source documentation) intolerance to or toxicity from these doses, in which case a dose between 10 and <15 mg, inclusive, may be used (See [Section 5.8](#)). The dose must have been stable for at least 4 weeks before first dose of study drug, and the dose must remain stable during the study.
 - Subjects should be on an adequate and stable dose of folic acid (not less than 5 mg weekly, unless higher doses would violate the local label) for at least 4 weeks prior to the first dose of investigational product or oral folinic acid (≥ 5 mg once per week) supplementation for at least 4 weeks prior to the first dose of study drug. Folic acid must be dosed per local standards of care stably for at

least 4 weeks before first study dose and the dose must remain stable during the study. In countries which do not have approved folic acid 1 mg or folinic acid 5 mg presentations, a regimen of folic acid of at least ≥ 5 mg weekly is acceptable.

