7.1.4.3. High Sensitivity C-Reactive Protein (CRP)

Samples for analysis of high sensitivity CRP (hsCRP) will be collected at the visits specified in the [Schedule of Activities](#). The samples will be shipped to and analyzed by a central laboratory. After randomization, the investigator and Pfizer study personnel directly involved in the conduct of the trial will be kept blinded of the results of this test.

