7.1.5.1. Simple Disease Activity Index (SDAI) Assessment

The SDAI is a continuous composite measure derived components of the ACR Core Dataset. The SDAI will be calculated using the following formula:

$$\text{SDAI} = \text{TJC (using 28 joints)} + \text{SJC (using 28 joints)} + \text{PtGA (0–10 cm scale)} + \text{PhGA (0–10 cm scale)} + \text{and hsCRP (mg/dL)}.^1$$

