3. ENDPOINTS AND BASELINE VARIABLES: DEFINITIONS AND CONVENTIONS

3.1. Primary Endpoint(s)

The primary endpoint for this study is change from baseline in SDAI at Week 8. The SDAI is a continuous composite measure derived from components of the ACR Core Dataset at baseline (Day 1), Weeks 1, 2, 4, 6, and 8.

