5.3.1. Binary Endpoint

For the binary response endpoints (eg, SDAI remission rates), subjects with missing values will be handled by:

- non-responder imputation (NRI) method, ie, setting any missing values to be non-responsive (0)
- will be used as observed (ie, excluding any missing values from analysis)

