6.2.2. DAS

For DAS28-3 (ESR), DAS28-3 (CRP), DAS28 -4 (ESR), and DAS28-4 (CRP), analysis of number of subjects with DAS28 remission (DAS<2.6) and DAS28 low disease activity (DAS28<3.2) at Weeks 4, 6, and 8:

- ITT population set
- Missing data imputation
 - Observed
 - NRI
- Normal approximation

Analysis of change from baseline in DAS28-3 (ESR), DAS28-3 (CRP), DAS28 -4 (ESR), and DAS28-4 (CRP)SDAI at Weeks 1, 2, 4, 6, and 8:

- ITT population set
- Missing data imputation – none (Observed)
- MMRM

6.2.3. hsCRP

Analysis of change from baseline in hsCRP at Weeks 1, 2, 4, 6, and 8:

- ITT population set
- Missing data imputation – none (Observed)
- MMRM

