Appendix 3. DATA DERIVATION DETAILS

A patient is said to have achieved the ACR20 criteria⁺ when all of the following bulleted points are true:

- A 20% improvement from baseline in the tender/painful joint count (TCJ28).
- A 20% improvement from baseline in the swollen joint count (SJC28).
- A 20% improvement from baseline in *at least 3* of the following 5 variables:
 1. PhGA of Arthritis;
 2. PAAP VAS;
 3. PtGA of Arthritis VAS;
 4. HAQ disability index;
 5. Results of ESR or CRP blood test (both of which test for inflammation).

ACR50 and ACR70 are defined analogously.

There are many forms of the DAS. The DAS used in this study is the DAS using the 28-count subsets of tender/painful joints and swollen joints, together with either CRP or ESR, to derive the DAS28-3 (CRP), DAS28-4 (CRP), or DAS28-3 (ESR) and DAS28-4 (ESR), which are calculated using the following formulae, respectively:

$$\text{DAS28-4(ESR)} = (0.56 * \text{sqrt(TJC28)} + 0.28 * \text{sqrt(SJC28)} + 0.70 * \text{ln(ESR)} + 0.014 * \text{GH}$$

$$\text{DAS28-3(ESR)} = [0.56 * \text{sqrt(TJC28)} + 0.28 * \text{sqrt(SJC28)} + 0.70 * \text{ln(ESR)}] * 1.08 + 0.16$$

$$\text{DAS28-4(CRP)} = 0.56 * \text{sqrt(TJC28)} + 0.28 * \text{sqrt(SJC28)} + 0.36 * \text{ln(CRP+1)} + 0.014 * \text{GH} + 0.96$$

$$\text{DAS28-3(CRP)} = [0.56 * \text{sqrt(TJC28)} + 0.28 * \text{sqrt(SJC28)} + 0.36 * \text{ln(CRP+1)}] * 1.10 + 1.15$$

where TJC28 is number of painful joints out of 28 joints, SJC28 is number of swollen joints out of 28 joints, GH is the general health or patients' global assessment of disease activity on a 100 mm VAS, ln is the natural logarithm, ESR is in mm/first hour, and CRP is in mg/L.

Handling Missing Joint Counts:

- A missing painful/tender assessment or one NOT DONE at *baseline* is set to “not painful/tender”;
- A missing swollen assessment or one NOT DONE at *baseline* is set to “not swollen”;

- A missing painful/tender assessment or one NOT DONE *post baseline* is set to “painful/tender”;
- A missing swollen assessment or one NOT DONE at *post baseline* is set to “swollen”.

Note that joints marked NOT APPLICABLE are not to be counted in the summation of swollen and painful/tender joints at baseline and post baseline.

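### SAP 5.3 turns below-limit hsCRP into missing with no visible exception, so very low CRP could cost a subject the SDAI or DAS28 (CRP) score; the issue is minor and one sentence removes it

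*SAP*

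**What the plan says.** - **Below-limit results.** SAP 5.3: "Unless there is an explicit instruction, missing values will be used for lower limits of detection and quantitation". The sentence is not confined to safety laboratory data.
- **SDAI.** Protocol 7.1.5.1 defines it as an unweighted sum of two 28-joint counts, two global assessments on a 0 to 10 scale "and hsCRP (mg/dL"). SAP 3.1 describes it as "derived from components of the ACR Core Dataset at baseline (Day 1), Weeks 1, 2, 4, 6, and 8".
- **Other uses of hsCRP.** The two CRP versions of DAS28 in SAP Appendix 3 contain it, and SAP 6.2.3 plans "Analysis of change from baseline in hsCRP at Weeks 1, 2, 4, 6, and 8".
- **Component rules.** Appendix 3 has a block headed "Handling Missing Joint Counts", and SAP 5.3.2 defers to the developers' rules for patient-reported scales. Neither place has a rule for CRP.
- **Binary endpoints.** SAP 5.3.1 plans an as-observed analysis and an NRI analysis, the latter by "setting any missing values to be non-responsive (0").
- **Assay.** Protocol 7.1.4.3: "The samples will be shipped to and analyzed by a central laboratory". Neither document gives a detection or quantitation limit. Inclusion criterion 8 requires hsCRP of at least "7 mg/L at screening performed by the central laboratory", with a re-test allowed.

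**The concern.** A very low CRP is a good result. If the general rule is applied to hsCRP and a missing component makes the composite missing, a subject with such a result has no Week 8 SDAI. That subject then contributes nothing to the Bayesian ANCOVA, which takes one change score per patient (SAP Appendix 4), and counts as a failure for SDAI and DAS28 (CRP) remission and low disease activity under NRI. The hsCRP endpoint loses its lowest values. Subjects enter with raised CRP, so such values should arise mainly on treatment and plausibly more often on active. An outcome would then be lost over a term that is almost nothing in the sum.

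**Working it through.** **1. The plan's own figure.** Protocol 9.1 assumes 30 active and 20 placebo completers, a difference of 13 and an SD of 14, and claims power over 90%. The standard error is 14 × √(1/30 + 1/20) = 4.04 and 13/4.04 = 3.22. Power is Φ(3.22 − 1.96) = 89.6% two-sided at 5%, or Φ(3.22 − 1.645) = 94.2% one-sided. This reproduces the claim closely enough, and these inputs are used below.

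**2. Size of the term.** hsCRP enters SDAI in mg/dL with weight 1, so a value below a limit of L mg/L contributes less than L/10.
- Assumed L of 0.2, 0.5 and 1.0 mg/L gives under 0.02, 0.05 and 0.1 point.
- From the documents alone, the assay must be able to read 7 mg/L, so the term is under 0.7 point.

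**3. Loss if the rule is followed.** The documents give no assay limit, no hsCRP effect and no correlation of hsCRP with response. The following are therefore assumptions, used in a simulation of 2,000,000 subjects per setting, labelled weak / middle / strong hsCRP response:
- Log hsCRP: population median 10 / 10 / 8 mg/L; between-subject SD 0.8 / 0.9 / 1.0; visit-to-visit SD 0.5 / 0.5 / 0.6.
- Entry if the screening value or one re-test is at least 7 mg/L; Day 1 is a fresh value.
- Week 8 median fall on active 50 / 60 / 75% (SD 0.6 / 0.8 / 1.0 log units); on placebo 10 / 10 / 20%.
- Correlation of hsCRP fall with SDAI improvement 0.3 / 0.4 / 0.5.
- SDAI improvement 13.7 on placebo (the mean of the SAP's placebo prior) and 26.7 on active, SD 14; baseline SDAI mean 40, SD 12.
- A subject is lost if hsCRP is below L on Day 1 or at Week 8.

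True low-disease-activity difference (SDAI of 11 or less): Week 8 SDAI has SD √(12² + 14²) = 18.4. The rates are Φ((11 − 13.3)/18.4) = 45% on active and Φ((11 − 26.3)/18.4) = 20% on placebo, a difference of about 25 percentage points.

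| Assumed limit | Active lost, % | Estimated SDAI difference (true 13) | NRI low-disease-activity difference, points (true about 25) |
|---|---|---|---|
| 0.2 mg/L | 0.0 / 0.2 / 2.0 | 13.0 / 13.0 / 12.7 | 24.7 / 24.8 / 23.3 |
| 0.5 mg/L | 0.4 / 1.7 / 8.7 | 13.0 / 12.8 / 12.1 | 24.5 / 23.8 / 19.1 |
| 1.0 mg/L | 2.7 / 6.6 / 19.7 | 12.8 / 12.5 to 12.6 / 11.3 to 11.8 | 23 / 21 / 13 to 15 |

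The ranges in the last row reflect the spread of hsCRP change on placebo, from narrower than on active (placebo loss at most 1.4%) to equal (4.5% in the strong setting). The upper rows use the narrower spread; an equal spread moves them less.

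**4. Effect on the primary verdict.** SAP 5.1 requires a posterior probability above 90% that Δ* exceeds zero. Use the placebo prior N(13.7, 25), a normal approximation, and a true placebo mean equal to the prior mean.
- Placebo posterior variance: 1/(1/25 + 20/196) = 7.04. Weight on the data: 7.04 × 20/196 = 0.718.
- With n active subjects: posterior SD = √(7.04 + 196/n); sampling SD = √(0.718² × 196/20 + 196/n).
- Chance of passing = Φ((difference − 1.282 × posterior SD)/sampling SD).

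| Case | n active | Posterior SD | Sampling SD | Chance of passing |
|---|---|---|---|---|
| No loss, difference 13 | 30 | 3.68 | 3.40 | 99.2% |
| Middle, 1 mg/L, difference 12.5 | 28 | 3.75 | 3.47 | 98.7% |
| Worst cell, difference 11.3 | 24 | 3.90 | 3.64 | 95.8% |

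**5. Error of half-limit substitution.** SDAI: at most L/20, or 0.01, 0.025 and 0.05 point at the three limits. DAS28-4 (CRP): at most 0.36 × ln(1 + L/2), or 0.03, 0.08 and 0.15 unit.

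**The case against.** The case against acting has four parts.

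1. **The harm needs a step the SAP does not state.** A reader might infer that the plan voids SDAI whenever hsCRP is below the limit. The text supports only that it could: no rule says what a missing component does to the score. An explicit hsCRP instruction may also sit in the programming document or in the sponsor's laboratory reporting standards, which are not available here. This stands, and the point is worded accordingly.
2. **Size rests on stacked assumptions.** Protocol 7.1.1 specifies a high-sensitivity method, and at 0.2 mg/L the effect is negligible. The largest figures need the highest limit, the largest fall and the strongest correlation together. This also stands.
3. **Other planned analyses help.** LOCF ANCOVA and MMRM draw on earlier visits for a lost Week 8 SDAI, and the binary endpoints are also analysed as observed. This is partial mitigation. None of these analyses restores the Week 8 value, and NRI still scores the subject as a failure.
4. **The direction is not certain.** The 7 mg/L minimum applies at screening only. In the simulated settings 21 to 26% of subjects are already below it on Day 1, though under 0.2% are below 1 mg/L. Bias toward no effect is likely, not guaranteed.

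A reader might also take the dash under missing data in the Bayesian row of Appendix 1 as a gap that calls for a new model. The documents do not support that. The single-visit model uses observed Week 8 values in effect, and LOCF, MMRM and a noninformative-prior version are already planned.

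**Conclusion.** The concern holds as a minor point. SAP 5.3 states a rule that, followed literally, makes low hsCRP missing, and the visible SAP neither exempts hsCRP nor says how SDAI and DAS28 (CRP) are then formed. The SDAI term is worth at most about 0.1 point only if the limit is 1 mg/L or less, which is an assumption.

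The consequence depends on that unstated limit. It is negligible at 0.2 mg/L. It becomes noticeable at 0.5 mg/L with a strong hsCRP response, and at 1 mg/L with a middle or strong one. The NRI response rates are the most exposed.

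It would be wrong to infer that the primary conclusion is in danger. At a true difference of 13 the chance of passing the 90% rule stays at about 96% even in the worst cell. The reason to act is that the remedy is nearly free whatever the assay.

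**What to change.** In SAP 5.3, state the hsCRP assay limit and add that a result below it is set to half the limit for SDAI, DAS28 (CRP) and change in hsCRP. If an instruction already exists in another document, cite it there instead.

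The cost is one sentence. The half-limit value is arbitrary, but its error is at most 0.05 SDAI point at a 1 mg/L limit. The sentence does not cover a lost or unusable sample, which remains ordinary missing data.

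Two optional additions are not needed for this point: writing Observed in the Bayesian row of Appendix 1, and a Bayesian repeated-measures sensitivity model.
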